- E-mail will be sent to eligible providers in batches until enough interviews have been scheduled and performed to reach data saturation

- *Verbal consent (waiver of written consent) requested for providers, since they will just be participating in semi-structured interviews.

Patients:

- Prospectively and/or retrospectively review clinic schedules for surgical and non-operative orthopedic spine providers
- To reach purposive sampling goals, some potentially eligible patients may be called prior to appointment date to notify them of the study, assess preliminary interest, and ask to plan staying 60-90 minutes after clinic visit in order to participate in study. Also offer to assist with parking expenses (eg parking validation ticket at CAM).
- Patients will officially be screened at the time of and/or after their orthopedic clinic visit to verify eligibility.
- *Written consent for patients when consent is obtained in clinic. Request the option for verbal consent if the participant is consented over the phone/Zoom.

Contact procedures / permission:

Providers:

- Participants will be e-mailed to be invited to participate.
- They will be asked to complete a brief “demographics” descriptive questionnaire.

Patients:

- Participants will be called or approached in person to be invited to participate.
- During the consent process, they will be asked whether they agree for e-mail and/or text messages to be sent to them. Based on their response, a link to the follow-up REDCap survey will be sent via e-mail and/or text message.

Participants will also be called, e-mailed, and/or text messaged as necessary for reminders to complete the survey.

2.b Randomization Method

No randomization method. No control group.

2.c Risks and Benefits

Risks:

You may experience one or more of the risks indicated below from being in this study. In addition to these, there may be other unknown risks, or risks that we did not anticipate, associated with being in this study.

Although very unlikely, subjects participating in this study may feel inconvenienced from completion of multiple surveys and/or uncomfortable answering some of the survey questions. This risk is minimal because participants will be informed of the estimated time commitment and general content of the survey questions before they consent to participate. The seriousness of this risk is low because participants can withdraw from the study at any time.

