The study PI ([name]) is one of over 15 spine care subspecialists within the WU Department of Orthopaedic Surgery. She and her colleagues manage patients with a range of sociodemographic backgrounds at multiple clinic sites across the St. Louis metro region including the Barnes-Jewish Center for Advanced Medicine, Barnes-Jewish Hospital Center for Outpatient Health, Barnes-Jewish West County Hospital, and the Barnes-Jewish Center for Advanced Medicine – South County. Furthermore, all of the WU Orthopedics spine patients complete depression and anxiety measures as standard care during each clinical encounter (PROMIS CAT Depression and Anxiety), and [name] research coordinator has specifically enrolled older adult orthopedic patients with spine conditions into mental health related research studies by using these measures as screening items. This patient base and the mental health screening measures will facilitate seamless recruitment of patient stakeholders with a range of self-reported depression and anxiety symptom severity. Additionally, [name] and several other spine providers have adequate clinical space to allow patient rooms to be used for research during clinic hours, and her team has experience recruiting, consenting, and enrolling patients into research studies in person and virtually (via phone or Zoom-HIPAA), from her own clinics and from those of her clinical colleagues. The in-person and virtual participation options will allow patients to participate in the semi-structured interview and usability testing in whichever format is preferred. When convenient for the participant, study recruitment, consent, and the interview can be completed within approximately one hour of the patient's clinical encounter.

E2 Schedule of Measurements

E3 Visit 1

Providers:

- Interviews will occur face-to-face (in a private room) or via Zoom, whichever the participant prefers. Interviews will be audio and possibly video recorded, using WU-HIPAA Zoom technology, handheld audio recorder(s), and/or other similar device. The recordings will be used to transcribe the interview conversation. After the interview, the recording will then be reviewed by a study team member, and all personal identifiers will be removed prior to being uploaded into Rev.com to be transcribed into text for qualitative analysis.

Patients:

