- Whenever possible, interviews will occur face-to-face immediately after the participant's orthopedic clinic visit (before the patient has left the clinic)
- If not possible, the participant will be given the option to return to campus for an in-person interview or to complete the study remotely via Zoom. Interviews will be audio and possibly video recorded, using WU-HIPAA Zoom technology, handheld audio recorder(s), and/or other similar device. The recordings will be used to transcribe the interview conversation. After the interview, the recording will then be reviewed by a study team member, and all personal identifiers will be removed prior to being uploaded into Rev.com to be transcribed into text for qualitative analysis.

Contact procedures / permission:

Providers:

- Participants will be e-mailed to be invited to participate.
-

Patients:

- Participants will be called or approached in person to be invited to participate.
- During the consent process, they will be asked whether they agree for e-mail and/or text messages to be sent to them. Based on their response, a link to the follow-up REDCap survey will be sent via e-mail and/or text message. Participants will also be called as necessary for reminders to complete the survey..

Proposed events chart:

Providers:

	Baseline	Follow-up
Intake survey	X	
Interview	X	X (If needed)

Patients:

	Baseline	1 Month
Intake survey	X	
Interview	X	
Usability testing of Wysa and	X	

printed guide		
System Usability Scale (printed guide)	X	
System Usability Scale (Wysa)	X	X
BADS-SF	X	X
CPAQ-8	X	X
Athens Insomnia Scale (AIS)	X	X
PROMIS measures	X (Standard care)	X
Follow-up survey		X

E4 Follow up.

A link to the follow-up REDCap survey will be emailed and/or text messaged to patient participants at one month. These surveys, listed in the chart above, will be the system usability scale (Wysa), BADS-SF, CPAQ-8, Athens Insomnia Scale (AIS), PROMIS measures, and a follow up survey. This will be for the patient participants only, and the only follow up that will occur.

E5 Safety and Adverse Events

5.a Safety and Compliance Monitoring

The research coordinator will document any adverse events reported and review these adverse events with the principal investigator as they arise.

If excessive adverse events are reported, the principal investigator will evaluate whether a participant should be removed from the study to ensure the study participants are not being injured.

5.b Definitions of Adverse Events

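### For patients consented after the day of their clinic visit, the events chart's baseline PROMIS score appears to predate both Wysa access and the behavioral-target baseline that F3 sets it against

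*Combined protocol and SAP*

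**What the plan says.** **Source of baseline PROMIS.** In the patient chart under E3, the baseline PROMIS cell reads "X (Standard care". It is the only baseline instrument labelled in this way; BADS-SF, CPAQ-8 and AIS have a plain X. E1 says that spine patients complete PROMIS Depression and Anxiety as part of usual care at every encounter. No section describes a separate research administration of PROMIS at enrolment.

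**Preferred timing.** E3 states: "Whenever possible, interviews will occur face-to-face immediately after the participant's orthopedic clinic visit". E1 adds that, when convenient, "study recruitment, consent, and the interview can be completed within approximately one hour of the patient's clinical encounter". Under 2.a, some patients are called beforehand; staff "ask to plan staying 60-90 minutes after clinic visit in order to participate in study".

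**Permitted later timing.** Section 2.a lets staff "Prospectively and/or retrospectively review clinic schedules for surgical and non-operative orthopedic spine providers". It also says: "Patients will officially be screened at the time of and/or after their orthopedic clinic visit to verify eligibility". On consent it adds: "Request the option for verbal consent if the participant is consented over the phone/Zoom". If an interview straight after the visit is not possible, E3 says "the participant will be given the option to return to campus for an in-person interview or to complete the study remotely via Zoom". No maximum time from the visit is stated.

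**Start of Wysa and follow-up.** Under 2.e, help with downloading the app comes after the patient agrees to take part. Access lasts one month. E4 sends the follow-up survey, which includes PROMIS, at one month, without saying from which date the month runs.

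**Use in analysis.** C1 (Aim 3) has PROMIS and the behavioral targets all collected at baseline and one month. F3 compares PROMIS change between high and low Wysa users. It also relates change in the behavioral targets to change in depression and anxiety.

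**The concern.** A correlation between two change scores is easiest to interpret when both changes run over the same interval and both start before the intervention. For a patient consented days or weeks after the visit, scales used only for research cannot have been completed before consent. Their baseline is therefore the later date. If PROMIS is taken from the encounter, as the chart indicates, its baseline is the earlier date. PROMIS change then combines a stretch without Wysa, during which orthopedic care is already under way, with the Wysa month. Target change covers only the period from enrolment.

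At stake is the Aim 3 search for mechanisms, which is meant to supply planning data for a later trial. The high/low comparison is exposed too, but only if late enrolment is more common in one group than in the other.

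**Working it through.** The plan states no sample size, effect or gap for Aim 3, so there is no figure to reproduce. The check has two parts: the order of dates that the text implies, and an illustration on assumed inputs.

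**1. Order of dates**

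| Step | Same-day patient | Patient consented later |
|---|---|---|
| Baseline PROMIS (E3 chart, E1) | Clinic visit | Clinic visit |
| Consent (2.a) | Same day | Visit + L days |
| BADS-SF, CPAQ-8, AIS (E3 chart) | Same day | Not before visit + L days |
| Wysa access (2.e) | After consent | Not before visit + L days |

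The documents do not limit L.

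**2. Share of the PROMIS interval before Wysa**

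Assume a 30-day month counted from enrolment. The share is L/(L + 30).

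- L about 1 hour: about 0.1%
- L = 7: 7/37 = 19%
- L = 14: 14/44 = 32%
- L = 28: 28/58 = 48%

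If the month were counted from the clinic visit instead, Wysa exposure before follow-up would be 30 − L days: 23, 16 or 2 days for these three gaps.

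**3. Effect on the F3 correlation (illustration only)**

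Let f be the share enrolled late and r the true correlation within the Wysa window. Let s be the SD of pre-Wysa PROMIS change relative to that of in-window change. Let a be the correlation of pre-Wysa PROMIS change with target change, and b its correlation with in-window PROMIS change. With unit in-window variances and equal mean change in late and same-day patients:

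r_obs = (r + f·a·s) / √(1 + f·(s² + 2·b·s))

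Take r = 0.50 and s = 1, the value obtained for a 4-week gap if variance grows in proportion to time.

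| Case | f = 25% | f = 50% |
|---|---|---|
| a = b = 0 (independent) | 0.50/√1.25 = 0.45 | 0.50/√1.50 = 0.41 |
| a = 0.4, b = 0.2 | 0.60/√1.35 = 0.52 | 0.70/√1.70 = 0.54 |
| a = −0.2, b = −0.3 (reversal) | 0.45/√1.10 = 0.43 | 0.40/√1.20 = 0.37 |

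The correlation can therefore move either way.

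**4. Dependence on the variance assumption**

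If variance grows with time, a 1-week gap gives s = √(1/4) = 0.5. At f = 25% the three cases are then 0.485, 0.521 and 0.478. If scores instead fluctuate around a stable level, s need not shrink with the gap. With s = 1, a = −0.25, b = −0.5 and f = 25%, r_obs = (0.50 − 0.0625)/√(1 + 0.25·(1 − 1)) = 0.4375, even at one week.

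**5. Comparison with sampling error**

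Fisher-z 95% limits for r = 0.50 are tanh(0.549 ± 1.96/√(n − 3)). For an assumed n = 20 they are 0.07 to 0.77; for n = 30, 0.17 to 0.73. Every shift above lies inside both intervals.

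**6. High/low user comparison**

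The shift equals mean pre-Wysa change × difference in late share. With an assumed 2 points and late shares of 40% and 20%, it is 2 × 0.20 = 0.4 points. It is zero if the shares are equal.

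**The case against.** **The reading is inferred.** The opening summary, C1 and D1 speak of one baseline at which participants complete both sets of measures. The content of the intake survey is not described, so a repeat of PROMIS at intake for later enrollees cannot be ruled out. The chart label may mean only that the usual same-day score is reused to spare patients. This stands as a limit on confidence. It does not remove the point, because those sections name no other source for baseline PROMIS and the chart does name one. If PROMIS is in fact repeated at intake, one line in the chart settles the matter.

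**No delay is documented.** The design favors same-day participation, and the text shows only that later enrolment is permitted, not how often or how late it happens. This stands. The late shares and gaps used above have no source in the plan.

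**The effect is small beside sampling error and confounding.** This also stands. F1 sizes the study by interview saturation, and with no control group, concurrent orthopedic care affects every change score whatever the baseline date.

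**Stronger readings that the documents do not support.**

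- A reader might infer that the PROMIS baseline is misplaced for all patients. For same-day patients the gap is about an hour.
- A reader might infer that the bias only weakens associations and is therefore conservative. That needs pre-Wysa change to be independent of the rest, which nothing in the plan establishes.
- A reader might infer that a gap of a week is harmless. That rests on the variance scaling shown to be fragile in step 4.
- A reader might infer that baseline Pain Interference and Physical Function are not collected, because E1 names only Depression and Anxiety. E1 is discussing recruitment and does not claim to list every standard-care domain. F3's target associations use depression and anxiety only.

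**Conclusion.** The point holds for patients consented on a day after their clinic visit. As the chart is written, their PROMIS change would begin before Wysa and before the behavioral-target baseline. The exploratory F3 associations could then be distorted in a direction that cannot be predicted, and the high/low comparison would be affected if late enrolment differs between the groups.

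The size cannot be derived from the documents. The illustrative range of 0.37 to 0.54 around a true 0.50 rests wholly on assumed shares, gaps and correlations. In a pilot of this kind the effect is probably below sampling error. The conclusion depends on reading the chart label together with E1, so confidence is medium. This is a worthwhile improvement to consider. It does not threaten the study: the qualitative and usability aims are untouched.

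**What to change.** Replace the baseline PROMIS entry in the patient events chart with wording such as: *Standard-care score if enrolled on the day of the clinic visit; otherwise PROMIS is given at intake together with BADS-SF, CPAQ-8 and AIS, all before Wysa access, using the same PROMIS instruments as at follow-up.*

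In addition:

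- Record the date of the baseline PROMIS score and the date on which Wysa access starts.
- State in E4 that the one-month follow-up is counted from the start of Wysa access.
- If Pain Interference or Physical Function is not in the standard-care set, give it at intake as well.

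The cost is chart wording, two dates and a few minutes of extra questionnaire time, mainly for later enrollees. PROMIS is already part of the study's one-month survey. H1 gives a start date of 12/1/2021. For anyone already enrolled without an intake PROMIS, the score cannot be recovered; only the dates can, and they would support a sensitivity analysis, for example one restricted to same-day enrollees. The change aligns the baselines but does not separate the effect of Wysa from that of concurrent orthopedic care.

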Questionnaire-8, and Athens Insomnia Scale) will be collected at baseline and one-month follow-up.²⁰⁻²⁶

C2 Rationale for the Selection of Outcome Measures

Depression and anxiety can worsen musculoskeletal pain and reduce the effectiveness of traditional orthopedic treatments. Nevertheless, addressing mental health is not currently a part of standard treatment for orthopedic conditions. The purpose of this study is to identify strategies to address mental health in the context of orthopedic care in a manner that is feasible, effective, and acceptable to patients and clinicians.

D Study Design

D1 Overview or Design Summary

This study will utilize qualitative cross-sectional and quantitative longitudinal methods. In semi-structured interviews, orthopedic providers and patients with spine conditions will discuss their overall perspectives, specific needs, and preferred solutions to addressing mental health impairment in the context of orthopedic care and research. In these sessions, patient stakeholders will also user test two specific mental health interventions: a customized version of a commercial digital mental health intervention (Wysa) and a prototype of a print-based mental health resource guide. The patient stakeholders will be provided one month of Wysa access, and they will complete baseline and follow-up measures related to usability, clinical effectiveness, and intermediate behavioral mechanisms through which Wysa is hypothesized to act. Wysa usage data will be obtained from the app company. Delivery of Wysa and the printed resource guide will be iteratively refined based on user feedback.^{13,29,34-42}

D2 Subject Selection and Withdrawal

Inclusion Criteria

- WU Orthopedics patients who are presenting to a spine specialist for neck and/or back pain (spine surgeon, physiatrist, or APP within either of those two divisions) for new or return evaluation
- 18+ years old
- Musculoskeletal pain for 3+ months

Exclusion Criteria

- Routine post-op visit, with no plans for further surgery at this time
- Endorses mental health crisis (active suicidal or homicidal ideation, psychosis)
- Cognitive impairment which would interfere with meaningful engagement with research interview, questionnaires, and/or intervention

2.a Subject Recruitment Plans and Consent Process

Providers:

- Eligible providers are already known, through departmental contacts

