Participants will have access to the Wysa app services for one month, and they can use any or all of the services as much or as little as they find useful. No one on the Washington University study team will read participants' chats to the Wysa chatbot. Any chats with a human Wysa well-being coach will remain between just the participant and their coach. The study team will only receive information on whether the participant used the Wysa app, how much they used each feature and/or found it helpful. Participants will be e-mailed and/or sent a text message to the follow-up survey link after one month. The surveys will ask them about their current level of wellness and whether they found the app helpful.

•

2.f Method for Assigning Subjects to Treatment Groups

No control group. Everyone in the provider group, gets the same treatment, and everyone in the patient group will get the same treatment.

E Study Procedures***E1 Screening for Eligibility***

Recruitment of orthopedic provider stakeholders:

Three of the study investigators are faculty members within the WU Department of Orthopaedic Surgery. As such, they have professional and personal relationships with the vast majority of the 70+ orthopedic clinicians and their support staff at WU. These relationships will facilitate a high rate of rapid recruitment from this group of stakeholders into the study. In addition to universal secure, virtual meeting capabilities among this group (Zoom-HIPAA), all orthopedic faculty members have dedicated, secure academic office space in which private semi-structured interviews can be conducted in person.

Recruitment of orthopedic patient stakeholders:

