- Suggest that the research places participants or others at a greater risk of harm (including physical, psychological, economic, or social harm) than was previously known or recognized.

5.d Data Collection Procedures for Adverse Events

The research coordinator will document any adverse events reported in a spreadsheet that is password protected and only available to be viewed by the study team.

All adverse events will be reviewed by the principal investigator as they arise.

5.e Reporting Procedures

Events will be reported per the Washington University Institutional Review Board Procedures.

5.f Adverse Event Reporting Period

Events that qualify for immediate reporting described above will be reported within the following timeframe:

- a. 10 working days of the occurrence of the event or notification to the PI or research team of the event.
- b. The death of a research participant should be reported within 1 working day of the occurrence of the event or notification to the PI or research team of the event.

Adverse events/other events that do not require immediate reporting will be provided to the IRB in summary format at the time of continuing review.

F Statistical Plan

F1 Sample Size Determination and Power

No power calculation was performed for this study because the primary aim involves a qualitative analysis. The sample size will be determined by reaching data saturation from the provider and patient stakeholder interviews.

F2 Interim Monitoring and Early Stopping

The Principal Investigator will take responsibility for monitoring patient safety. Patients in the study will be monitored on an as needed basis to assure that they are doing well.

Adverse events will be assessed by [name] to determine if they are serious, unexpected and related to the study procedures.

If a complication should arise, the patient would be previously instructed how to contact the research coordinator.

F3 Statistical Methods

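### No adverse-event question is described at any time point and F2's as-needed monitoring has no stated method, so the adverse-event count is likely to be incomplete

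*Combined protocol and SAP*

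**What the plan says.** **Recording.** Section E5, 5.a: "The research coordinator will document any adverse events reported", and adds that the principal investigator reviews them with the coordinator. Section 5.d: "The research coordinator will document any adverse events reported in a spreadsheet that is password protected". Section 5.b defines an adverse event broadly, covering any unfavorable sign, symptom or disease.

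**Monitoring.** F2: "Patients in the study will be monitored on an as needed basis to assure that they are doing well". The only reporting route it describes is this: "If a complication should arise, the patient would be previously instructed how to contact the research coordinator".

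**What the team can see.** Under 2.e, chatbot conversations are not read and coach conversations stay private. "The study team will only receive information on whether the participant used the Wysa app", together with how much each feature was used and whether it was found helpful.

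**Contacts.** The patient events chart has two columns, baseline and one month, and no adverse-event row. E4 lists the month-one instruments (System Usability Scale, BADS-SF, CPAQ-8, Athens Insomnia Scale, PROMIS measures and a follow-up survey) and calls this "the only follow up that will occur". According to 2.e, the surveys cover present wellness and the helpfulness of the app. The items of the follow-up survey are not reproduced.

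**Use of the count.** In 5.a, an excess of reported events leads the principal investigator to consider removing a participant. In 5.f, events that do not need immediate reporting go to the IRB in summary at continuing review. F3 plans no adverse-event analysis.

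**The concern.** D2 excludes patients in a mental health crisis at entry. Participants then have a month's access to an app that 2.e calls investigational. F2 states a purpose, assuring that patients are well, but the plan does not say how the team would learn that a patient was not. If events enter the record mainly when someone chooses to report them, a low count says as much about how events were collected as about what happened.

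The stake is safety oversight. The excess-events step in 5.a and the IRB summary in 5.f both work from the recorded events. A secondary stake is that the study prepares for a later trial, and a reader could take a low count as reassurance there, although no passage says the count will be used that way.

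**Working it through.** The documents give no figure to reproduce. F1 sets the sample size by data saturation, and no adverse-event rate or reporting share is stated. The check is therefore a comparison of sections: by what route could an event in the month of app access reach the record?

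| Possible route | What the plan describes | Set up to find adverse events? |
|---|---|---|
| Patient contacts coordinator (F2) | Patient told beforehand how to do so | Passive |
| As-needed monitoring (F2) | No schedule, trigger or method | Undefined |
| App chats (2.e) | Not seen by the study team | No |
| App usage data (2.e) | Use and helpfulness only | No |
| Month-one surveys (2.e, E4, events chart) | No adverse-event item described; follow-up survey items not shown | Not as described |
| Month-one PROMIS Depression and Anxiety (C1, E4) | Used in F3 for comparing heavier with lighter users and for associations | Could show worsening; no individual safety review stated |
| Standard-care PROMIS at clinic visits (E1) | Described as helping recruitment | Not tied to safety review |
| Reminder calls (2.a, E3) | To prompt survey completion | No |
| Notification of the PI or team (5.f) | Starts the reporting clock | Passive |

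Every defined route is either passive or not directed at adverse events. Set against the broad definition in 5.b, incomplete capture is the likely result.

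**Illustration only; every input is an assumption.** If a share r of true events is reported, the share missed is 1 − r: 75%, 50%, 25% and 0% for r = 0.25, 0.50, 0.75 and 1.00.

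With n patients, each having an event with probability p, the chance that none is recorded is (1 − p·r)^n. For n = 30:

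| p | r = 0.2 | r = 0.5 | r = 1 |
|---|---|---|---|
| 5% | 0.99^30 = 0.74 | 0.975^30 = 0.47 | 0.95^30 = 0.21 |
| 10% | 0.98^30 = 0.55 | 0.95^30 = 0.21 | 0.90^30 = 0.04 |
| 20% | 0.96^30 = 0.29 | 0.90^30 = 0.04 | 0.80^30 = 0.001 |

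The r = 1 column needs every survey returned and every event disclosed. With p = 10%, 70% return and no other reports, 0.04 becomes (1 − 0.10 × 0.70)^30 = 0.93^30 = 0.11. The table shows only that an empty record can be hard to interpret in a small cohort. It does not estimate the shortfall in this study.

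**The case against.** The case against is substantial, and most of it limits how far the point can go.

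- **A reader might infer that F2 contradicts E4 and 2.e.** It does not. F2 says monitoring is as needed and promises no visits or screening. The defect is an undefined procedure.
- **A reader might infer that events count only if the patient contacts the coordinator.** The text does not establish this. Sections 5.a and 5.d do not say who reports, 5.f allows for notification of the PI or team, and patients remain in orthopedic care. The unseen follow-up survey might contain an adverse-event item. The exact statement is that none is described.
- **A reader might infer that nothing at follow-up could reveal deterioration.** Month-one PROMIS Depression and Anxiety could. What is missing is any statement that individual scores are reviewed for safety.
- **A reader might infer that harms will certainly be under-counted, or by a given amount.** The documents support likely incompleteness of unknown size.
- **The consequence for the science is limited.** The aims concern implementation, usability and mechanisms. There is no control group, and no adverse-event rate is an endpoint.

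These objections narrow the claim but leave its core: no route that is described asks patients about adverse events, and F2's stated purpose has no procedure behind it. It is also fair that a month-one item does nothing about timing within the month and misses non-responders; that is a limit of the fix.

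**Conclusion.** The point holds as a gap in ascertainment. Adverse events are documented when reported, no question about them is described at any time point, F2's monitoring has no method or trigger, and no passage says month-one scores are reviewed for safety. The count used in 5.a and in the IRB summary is therefore likely to be incomplete, by an amount the documents do not allow to be calculated.

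This rests on two readings: that the word reported in 5.a and 5.d carries its ordinary passive sense, and that the follow-up survey has no adverse-event item. If it has one, saying so in 5.d resolves most of the point. No aim or planned estimate is affected. The change is a cheap improvement to safety oversight and to the completeness of the event count.

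**What to change.** 1. Add one structured adverse-event question to the one-month REDCap survey, covering worsening of mental health and events linked to the interview or the app. If the follow-up survey already asks this, describe the item in 5.d.
2. State in 5.a and 5.d that returned surveys, including PROMIS Depression and Anxiety, are reviewed for adverse events.
3. Report the event count with the number of patients who answered the item, so that a zero can be read against its denominator.
4. Reconcile F2 with 2.e and E4, so that the monitoring described is what the contacts and data flow allow.

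How a disclosed event is handled is for the investigators to set.

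**Cost.** One more survey item and coordinator time to review returns. The reported count may rise. Non-responders, and events while they are happening before month one, would still be caught only passively.
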